For patients identified in the setting of a 3-vessel qualifying diagnostic angiogram and successful PCI of a non-LM or non-LAD vessels in the same or subsequent procedure, randomization into the trial must occur within 90 days following the initial qualifying angiogram. The first “study” intervention must be performed within 14 days following randomization (see above Table for possible procedure options).

Randomization will be stratified by center, PCI of non-LM or non-LAD vessels within the prior 90 days, and type of vessels treated (1) LAD and Diagonal only; 2) LAD (or Left Main) and LCX or RCA; 3) LAD (or Left Main) and both LCX and RCA). The randomization scheme will be in random blocks of 4 and 6 within each stratum to maintain balance.

Randomization will be generated centrally and performed through a Web-based data collection system that automates the delivery of the randomization codes. The treatment assignment will be

sent to the site coordinator electronically, in a secure fashion, and electronic verification of the treatment assignment will be required before proceeding with the treatment intervention. From that point on, primary efficacy will be analyzed by intention-to-treat; that is, the patients will be grouped by their assignment at randomization whether or not they actually received the treatment to which they were assigned.

MASKING

Neither patients nor investigators will be blinded to treatment assignment due to the nature of treatment interventions. Clinical and CCC investigators will, however, be blinded to all data from other clinical sites, except serious unexpected adverse events (SAEs) for IRB/REB reporting purposes. The DCC Research Nurse will be blinded to treatment assignment during follow-up telephone calls and will be blinded to aggregate outcomes data. MACCE events will be adjudicated by the independent CEC and trial oversight will be provided by an independent Data & Safety Monitoring Board (DSMB).

TREATMENT INTERVENTIONS

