Note: Sudden unexpected cardiac death, involving cardiac arrest, often with symptoms suggestive of myocardial ischemia, and accompanied by new ST-segment elevation or new LBBB, and/or evidence of fresh thrombus by coronary angiography and/or autopsy, with death occurring before blood samples obtained, or at a time before the expected appearance of cardiac biomarkers in blood will be classified as a mortality due to peri-procedural MI.

○ *Unplanned Revascularization (adjudicated)*

(a) An unplanned revascularization procedure is defined as any PCI or CABG procedure performed that is an entirely new procedure due to ischemia not included in the pre-specified revascularization strategy, or (b) was included in the pre-specified revascularization strategy as a planned staged procedure, but was performed >90 days after the first revascularization procedure after randomization, or (c) that is a repeat intervention of a previously performed study-related revascularization. Determination as to whether the revascularization procedure involves an original target vessel and lesion or a new (non-target) vessel and lesion will be made by the CEC whenever possible.

Ischemia-driven Unplanned Revascularization

Ischemia-driven *unplanned* revascularization procedures will be assessed. All *unplanned* revascularization procedures will be reviewed and adjudicated by the CEC to determine if they are ischemia-driven. Revascularization will be considered ischemia-driven if the diameter stenosis of the revascularized coronary segment is $\geq 50\%$ or new thrombus and/or ulceration is present, and if any of the following criteria for ischemia are met: i) A positive functional study corresponding to the area served by the target lesion; or ii) Ischemic ECG changes at rest in a distribution consistent with the target vessel; or iii) Typical ischemic symptoms referable to the target lesion; or iv) IVUS of the target lesion with a minimal lumen area (MLA) of $\leq 4 \text{ mm}^2$ for non-left main lesions or $\leq 6 \text{ mm}^2$ for left main lesions; or v) FFR of the target lesion ≤ 0.80 or iFR of the target lesion < 0.90 . A target lesion revascularization for a diameter stenosis less than 50% might also be considered ischemia-driven by the CEC if there was a markedly positive functional study or ECG changes corresponding to the area served by the target lesion.

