Randomization

Must be completed

- (a) within 90 days of the 3-vessel qualifying angiogram for patients identified in the setting of a diagnostic angiogram, or*
- (b) within 90 days following the qualifying 3-vessel angiogram for patients also undergoing a PCI of a non-LAD and non-LM vessel prior to randomization. (See table under Randomization Section)*

The first study intervention is recommended to be performed within 72 hours post randomization and must be performed within 14 days following randomization.

Randomization to the treatment assignment will be generated by the EDC system once the checklist of inclusion and exclusion criteria has been completed and verified and the planned revascularization strategy form has been completed. For the purpose of the primary analysis, patients are considered enrolled in the study once they are randomized and an identification code is generated.

Revascularization Plan

Prior to randomization

The surgical and percutaneous revascularization plan will be described for both HCR and PCI-only revascularization *prior to randomization*. This plan may be revised within 24 hours of the first procedure after randomization to reflect procedural complications, should they occur. Any revascularization procedures deviating from the final revascularization plan in place 24 hours after the first procedure will be considered unplanned revascularization procedures.

Note: Any revascularization procedure that is done during a planned revascularization procedure will NOT be considered an unplanned procedure. E.g.: planned minimally invasive LIMA-LAD procedure becomes complicated by inferior ischemia requiring conversion to an open procedure and RCA bypass; or planned PCI after minimally invasive

LIMA-LAD procedure demonstrated LIMA-LAD graft occlusion requiring PCI; or planned PCI of the LCX results in a LM dissection requiring a LM stent. However, CABG complications that result in separate **unplanned** PCI or CABG procedures, and PCI complications that result in separate **unplanned** PCI or CABG procedures, will be considered unplanned procedures and endpoint events.

Angina Class - Canadian Cardiovascular Society Classification (CCSC)

Following determination of eligibility and within 14 days prior to randomization

The presence of angina will be assessed, and when present, classified according to the CCSC scale and documented on this form. CCSC classification scheme is detailed in Appendix I.

NYHA Class

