Sample size for this study was determined based on the following operating characteristics: (a) two sided type I error fixed at 0.05, (b) 80% power, (c) minimum follow-up of 5 years, 2-year enrollment period with uniform enrollment (d) 5-year MACCE rate in the PCI group of approximately 25%, (e) expected 5-year MACCE relative rate reduction in the HCR group of $\geq 20\%$, (f) drop-in (HCR to PCI) and drop-out (PCI to HCR) rates of approximately 0.5% and 2% respectively, and (g) loss to follow-up by the end of the study of 15%. Under the above assumptions it is estimated that 530 events (or 2354 patients) will be required to detect a relative decrease in MACCE of $\geq 20\%$ in the HCR compared to the PCI group. This is a reasonable improvement based on estimates from recent studies.²⁵⁻²⁸

Interim Monitoring Guidelines

The objectives of interim monitoring are to (1) monitor for safety, (2) track participant accrual rates, and (3) monitor the primary and secondary outcomes for early evidence of efficacy, harm or futility. To accomplish this, summaries of data quality, accrual, adherence, distribution of

baseline factors, safety, study endpoints and other analyses as requested will be prepared for review by the DSMB. A single interim analysis and one final analysis are planned for this trial, for a total of two analyses. The interim analysis will be conducted when 0.5 fraction of the total number of events have been observed. This interim analysis will evaluate the composite rate of adjudicated death, stroke or MI (excluding unplanned repeat revascularization), as the endpoint is being conducted for safety, rather than efficacy, purposes. We will use an alpha-spending O'Brien-Fleming sequential procedure as a guideline for decision-making. At the interim analysis the value of the test statistic will be compared with the alpha spending function critical value. The p-values for the interim monitoring analysis and the final analysis are, 0.0031, and 0.05, respectively.

Stopping Rule

We do not anticipate stopping the trial for evidence of early efficacy or futility at the time of the interim analysis. The collection of 5-year follow-up information on all patients enrolled in the trial is necessary to provide a comprehensive overview of the relative safety and effectiveness of the two randomized strategies.

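### The Revascularization Plan rule can count a non-ischemic crossover as a primary endpoint event, while the endpoint definition would not; the sections need one rule

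*Combined protocol and SAP*

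**What the plan says.** Unplanned revascularization is one of the four components of MACCE, the primary endpoint. Several sections bear on what counts.

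- **Data Collection, Revascularization Plan.** Plans for both HCR and PCI-only treatment are written before randomization. On revision: "This plan may be revised within 24 hours of the first procedure after randomization to reflect procedural complications, should they occur". Then: "Any revascularization procedures deviating from the final revascularization plan in place 24 hours after the first procedure will be considered unplanned revascularization procedures". A note exempts extra work done during a planned procedure.
- **Treatment Interventions, opening paragraph.** Endpoint events are unplanned procedures driven by ischemia, whenever they occur, and any procedure more than 90 days after the first one following randomization.
- **Definitions and Measurement of Endpoints, Unplanned Revascularization.** There are three limbs: (a) "an entirely new procedure due to ischemia not included in the pre-specified revascularization strategy"; (b) a planned stage done after 90 days; (c) a repeat of an earlier study revascularization. Stages declared within 24 hours and done within 90 days are exempt.
- **Long-term Patient-Reported MACCE & QoL.** Once the planned procedures are complete, any further PCI or CABG is a MACCE, with no mention of ischemia.
- **Treatment Assignments.** Analysis is by intention to treat: "the patients will be grouped by their assignment at randomization whether or not they actually received the treatment to which they were assigned".
- **Power and Sample Size.** The design allows for "drop-in (HCR to PCI) and drop-out (PCI to HCR) rates of approximately 0.5% and 2% respectively". The Abstract gives the same two figures as annual rates.

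None of these sections says how a procedure belonging to the other arm's strategy is scored.

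**The concern.** Take a patient assigned to HCR who declines surgery and has every vessel stented, including the LAD. The LAD stent is not part of the HCR plan, and no procedural complication permits a revision. On the words of the Revascularization Plan section this is an unplanned revascularization. Because the first procedure is due within 14 days of randomization, it would be a primary event in the first two weeks.

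The rule bites most directly on a staged patient. PCI first with surgery later is an allowed HCR sequence. If that patient refuses surgery more than 24 hours after the first stage and has the LAD stented instead, the procedure departs from the plan in force at 24 hours. The Treatment Interventions text and limb (a) would not score it unless it was due to ischemia.

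Only one arm requires surgery and treatment is not masked, so crossover is unlikely to be equal between arms; the sample size itself assumes that it is not. If crossovers are scored, part of the primary result measures whether the assigned strategy was delivered, mixed with death, MI, stroke and true failures of revascularization.

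**Working it through.** **Inputs.** From Power and Sample Size: two-sided 5% error, 5-year MACCE of 25% with PCI, a 20% relative reduction (so 20% with HCR), 530 events, 2354 patients, and crossover of 2% (PCI to HCR) and 0.5% (HCR to PCI). Allocation is 1:1, so 1177 per arm.

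**The plan's own figure.** 1177 × (0.25 + 0.20) = 529.65, or 530 events. HR = ln(0.80)/ln(0.75) = 0.776. Diluting each arm once for crossover gives PCI 0.98 × 25% + 0.02 × 20% = 24.9%, HCR 0.995 × 20% + 0.005 × 25% = 20.025%, and HR 0.780. Freedman's formula, (1.96 + 0.8416)² × (1.780/0.220)², then gives 516 events (using the unrounded HR), within 3% of 530. This leaves out the 15% loss to follow-up.

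**Formulas when a crossover is scored.** With first-procedure crossover shares cP and cH and true 5-year rates qP and qH:

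- pP = cP + (1 − cP) × qP; pH = cH + (1 − cH) × qH
- HR = ln(1 − pH)/ln(1 − pP)
- D = 1177 × (pP + pH)
- Power = Φ(√(D/4) × |ln HR| − 1.96)

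**Worked case, 2% and 0.5%.** pP = 0.02 + 0.98 × 0.25 = 0.265. pH = 0.005 + 0.995 × 0.20 = 0.204. HR = ln(0.796)/ln(0.735) = 0.741. D = 1177 × 0.469 = 552. Power = Φ(3.52 − 1.96) = 94%.

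**Same shares, no true effect.** pP = 0.265, pH = 0.25375, HR = 0.951, D = 611. Chance of a significant result for HCR = Φ(0.625 − 1.96) = 9.1%, against 2.5%.

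| True rates, PCI / HCR | PCI to HCR | HCR to PCI | Scored? | HR | Result |
|---|---|---|---|---|---|
| 25% / 20% | 0 | 0 | – | 0.776 | power 83% |
| 25% / 20% | 2% | 0.5% | no | 0.780 | power 81% |
| 25% / 20% | 2% | 0.5% | yes | 0.741 | power 94% |
| 25% / 20% | 0.5% | 1% (assumed) | yes | 0.80 | power 75% |
| 25% / 20% | 0.5% | 2% (assumed) | yes | 0.83 | power 58% |
| 25% / 20% | 0.5% | 5% (assumed) | yes | 0.94 | power 12% |
| 25% / 20% | 2% | 2% (assumed) | yes | 0.790 | power 80% |
| 25% / 25% | 2% | 0.5% | no | 1.00 | false HCR win 2.5% |
| 25% / 25% | 2% | 0.5% | yes | 0.951 | false HCR win 9.1% |
| 25% / 25% | 0.5% | 5% (assumed) | yes | 1.16 | rejects equality 46% |

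Equal crossover of 2% in both arms gives HR 0.790 if scored and 0.784 if not, so the bias comes from inequality between the arms.

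**What it would take to remove or manufacture the effect.** To erase 25% versus 20%: 0.20 + 0.80c = 0.25, so c = 6.25% net HCR-to-PCI crossover, about 74 of 1177 patients; if PCI crossover is 2%, the figure is 8.1%. To produce HR 0.776 from no effect: 1 − c = 0.75^(1/0.7757 − 1) = 0.920, so c is about 8.0% net PCI-to-HCR crossover.

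**Upper bound from the Abstract's annual rates.** Over five years, 1 − 0.98⁵ = 9.6% and 1 − 0.995⁵ = 2.5%. If every one were scored, the null HR would be 0.805, with about an 82% chance of a false HCR win. Annual crossovers do not all fall at the first procedure, so this is a ceiling and not an estimate.

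**The case against.** The strongest reply is that the formal definition governs. The events committee is charged with applying the pre-specified definitions, and a crossover by preference meets none of the three limbs plainly. The Revascularization Plan section never mentions crossover, and its sentence reads most naturally as covering procedures after the first. Because plans for both strategies are on file before randomization, the other arm's procedure may already be planned. The Percutaneous Interventions section and the endpoint definition also let stages be declared within 24 hours without requiring a complication.

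Much of this stands. A reader might infer that the plan definitely scores crossovers as MACCE. The documents do not support that: it is a literal reading of one sentence against the endpoint definition.

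A reader might also infer that scoring would contradict intention to treat or the crossover allowance. It would not. Intention to treat fixes the group in which a patient is analysed, and the allowance enters only the sample size. A patient can stay in the assigned arm and also have an event. Neither section settles the scoring.

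The reply does not remove the conflict. The committee reviews all unplanned procedures to decide which were ischemia-driven, and ischemia-driven revascularization is a separate secondary endpoint, so the unplanned category appears wider than the ischemia-driven one. The long-term follow-up section also has no ischemia condition. The 24-hour allowance does not help a patient who switches later than that.

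**Conclusion.** The sections give different answers for a non-ischemic crossover within 90 days: the Revascularization Plan rule, read literally, scores it, while Treatment Interventions and limb (a) do not. If crossovers are scored and unequal by arm, the primary comparison is biased. At 2% and 0.5% the HR moves from 0.776 to 0.741 and the false-win rate for HCR from 2.5% to about 9%. With more crossover out of the surgical arm the bias runs the other way, and power falls to 58% or 12% at assumed shares of 2% or 5%.

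It would go too far to say that crossover alone creates or erases the treatment effect at the plan's stated rates. Erasing it needs about 6% net HCR-to-PCI crossover, against a stated 0.5%; creating it needs about 8% net in the other direction.

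These figures assume constant hazards, crossover unrelated to risk, no losses, five years of follow-up for all, and each crossover scored once as an early event. Reading 2% and 0.5% as first-procedure shares is itself an assumption, since the Abstract calls them annual. The larger HCR-to-PCI shares are not in the documents. This should be fixed; it is a clarification of the endpoint and does not undermine the design.

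**What to change.** Reconcile Treatment Interventions, Unplanned Revascularization (including its paragraph on staged procedures), Revascularization Plan and the long-term MACCE section around one rule, repeated in the events committee charter:

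- *Replacing all or part of the assigned strategy with the other arm's pre-randomization plan, within 90 days of the first procedure after randomization, is not an unplanned revascularization solely because it is a crossover.*
- *It still counts if the committee adjudicates it as ischemia-driven and unplanned, or as a repeat intervention on a treated lesion.*
- *The patient stays in the randomized arm.*

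This covers both the crossover at the first procedure and the staged patient who switches more than 24 hours later. Every patient enters with an indication for revascularization, so the charter should also say that this indication alone does not make a crossover ischemia-driven. Report crossovers by arm, and add one sensitivity analysis that counts all of them as events.

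The cost is a short wording change and one extra analysis. The downside is that a non-ischemic crossover reflecting failure to deliver the assigned strategy counts only in the sensitivity analysis.

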By design, patients in the HCR group will undergo planned staged procedures, and patients in the PCI group may or may not undergo planned staged procedures. The treatment strategy for staged procedure will be collected at the time of the first index procedure. Regardless of treatment assignment (HCR or PCI group), the revascularization strategy for staged procedures must be completed (in all cases) within *90 days* after the first revascularization intervention after randomization, with ≤ 60 days recommended. Unplanned ischemia-driven procedures at any time, and all procedures performed >90 days after the first post-randomization revascularization intervention will be considered endpoint events.

To minimize ascertainment bias in the identification of peri-procedural MI, baseline cardiac biomarkers (CK-MB and/or Troponin T or I) and an electrocardiogram (ECG) must be performed in all patients prior to CABG and PCI. For patients with stable CAD, the baseline biomarkers may be sent at the time of the first procedure, before revascularization. An ECG must be repeated once within 24 hours after each revascularization procedure, and the biomarkers must be repeated at least twice within 24 hours after each procedure (at 12 ± 4 hours and at 24 ± 4 hours, or at discharge if sooner than 24 hours).

Hybrid Coronary Revascularization

HCR is defined, for the purposes of this trial, as a planned off-pump, minimally invasive (sternal-sparing) isolated LIMA-LAD revascularization, combined with percutaneous revascularization of at least one non-LAD target. The revascularization targets and procedural timing strategy to be utilized should be outlined prior to the initial revascularization procedure. Three possible timing strategies may be used: surgery followed by PCI on separate calendar days, PCI followed by surgery on separate calendar days, or concomitant (simultaneous) PCI and surgery (defined as: a. PCI followed by CAGB in the same room on the same day, or b. CABG followed by PCI in the same room on the same day, or c. PCI followed by CABG in different rooms on the same day, or d. CABG followed by PCI in different rooms on the same day). The specific strategy adopted will be collected and categorized. The complete revascularization strategy, if staged, must be completed within *90 days* of the first revascularization intervention (≤ 60 days preferred).

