Confidentiality of all patient records will be maintained according to HIPAA or PIPEDA guidelines. Study Investigators, site IRBs/REBs, the DCC (InCHOIR), the CEC, the FDA and the NHLBI may review source documentation for enrolled patients as necessary, but all unique patient and hospital identifiers will be removed prior to review. If the results of this study are published, the data will be presented in aggregate, with all patient identifiers removed.

HIPAA or PIPEDA Certification

All investigators and coordinators must provide documentation that they have successfully completed the institutional requirements to ensure patient rights, privacy and security under HIPAA or PIPEDA.

SITE INITIATION

IRB/REB approval and the clinical study agreement between the clinical site and the DCC must be signed and executed prior to the site initiation. Additionally, applicable CVs and other regulatory documentation must be on file with the DCC prior to site initiation. A representative from the DCC will conduct a site initiation teleconference prior to enrollment of the first patient. The surgeon(s), interventional cardiologist(s), and study coordinator will be required to attend the initiation.

DATA COLLECTION

For clinical sites participating in the STS registry, data collection will be done using the STS registry dataset. For clinical sites that are not part of the STS registry, and for patients randomized to PCI, data collection will be done at the site.

Screening Data Collection

Screening Registration Form

Prior to informed consent

Prior to approaching a patient to begin the informed consent process, the study personnel will review data on prospective patients to determine eligibility for inclusion in the trial. All pre-screened patients (patients who are not consented) who are not enrolled are recorded in the Screening Registration form in the EDC. The data collected is HIPAA compliant and does not include patient identifiers but does include screening quarter, screening year, age, gender, race and reason not eligible or not enrolled.

Informed Consent

Prior to screening data collection and all protocol defined procedures

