Following determination of eligibility and within 14 days prior to randomization

The presence of heart failure will be assessed, and when present, classified according to the NYHA scale. NYHA classification will be determined by investigative center personnel and documented on the “New York Heart Association Classification” form. The NYHA classification scheme is detailed in Appendix III.

Quality of Life

Following determination of eligibility and within 14 days prior to randomization

The SF 12 and EuroQol (Appendix II) questionnaires will be completed by the patient to assess quality of life.

Pre-intervention Existing STS Registry Data Extraction (collected by sites if not participating in STS or for patients randomized to PCI group)

Angiogram

Data partially extracted from the STS Registry database

Data regarding the coronary anatomy, including the number of lesions, degree of coronary obstruction and SYNTAX score will be extracted from the STS registry database.

Demographics

For all patients screened, the date of birth, race, ethnicity, sex, and insurance will be captured.

Medical History

Data partially extracted from the STS Registry database

Information pertaining to the medical history, with particular focus on cardiovascular history, will be extracted from the STS registry database. The data collection includes, but is not limited to previous myocardial infarction and coronary revascularization, AICD and pacemaker therapy, stroke and other comorbidities such as diabetes, dialysis and peripheral vascular disease. Information regarding the current cardiac condition is also captured, including symptoms and severity of cardiac disease and the patient's current height and weight.

Laboratory Assessment

Data partially extracted from the STS Registry database

Data regarding the following laboratory values prior to index coronary revascularization will

- CK MB (creatinine kinase- myocardial band) and/or Troponin I or T (ng/mL)
- Hematocrit (%)
- Creatinine (mg/dL)

Treatment Intervention

The assigned study coronary revascularization intervention (or first revascularization intervention, for staged procedures) are *recommended to be performed within 72 hours post randomization, and must be performed within 14 days following randomization*. (See Randomization section)

Procedural and Peri-Procedural STS Registry Data Extraction (collected by sites if not participating in STS or for patients randomized to PCI group)

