The following will be collected for all hospitalizations required to complete the original planned revascularization strategy, if staged.

Medications

Data regarding medication use within 24 hours prior to, during the revascularization procedure or within 24 hours after the procedure, including antiplatelet and antithrombin agents, beta blocker, and ACE inhibitors, ARBs, aldosterone antagonists, and statins, will be collected at the sites. This data will be collected whenever possible for all subsequent revascularization procedures.

Laboratory Assessment

Data partially extracted from the STS Registry database

Data regarding the following laboratory values after the index coronary revascularization will be extracted from the clinical registry databases:

- CK MB and/or Troponin I or T (ng/mL)

PCI Procedure

Data regarding the index PCI procedure(s) will be provided by the site coordinators. Information to be collected includes, but is not limited to, the status of the procedure (e.g., elective, urgent, emergency, salvage), indications for the procedure, the percutaneous intervention(s) performed, and intra and post-procedural events.

Index Surgical Procedure

Data partially extracted from the STS registry database; HCR Group ONLY. Additional data to be supplied by cardiac surgical investigator

Data regarding the surgical intervention for the HCR procedure will be extracted from the STS dataset, including but not limited to the status of the procedure (e.g., elective, urgent, emergent, and emergent salvage), details regarding the anesthesia and intra-operative interventions, bypass pump use, conduit and harvest technique, anastomoses, concomitant procedures, and intra-operative blood use and complications if applicable. Modest additional

Hospitalization & MACCE Events

Limited information about the index revascularization procedure(s) and hospitalization will be extracted from the STS registry dataset including length of stay, transfusion requirements, repeat procedures, and discharge disposition when possible. Information regarding MACCE events that occur during study-procedure related hospitalizations will also be extracted from the STS registry when possible. Limited source documentation pertaining to the MACCE event will be collected and uploaded into the EDC as detailed in the trial Manual of Procedures (MOP).

Index Hospital Costs

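### At STS sites, the first-line source of in-hospital MACCE and post-procedure biomarkers differs by arm: registry extraction for HCR patients, site collection for PCI patients

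*Combined protocol and SAP*

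**What the plan says.** The opening of Data Collection sets the general rule: "For clinical sites participating in the STS registry, data collection will be done using the STS registry dataset". For sites outside the registry it names a different source, "and for patients randomized to PCI, data collection will be done at the site". The heading of the procedural and peri-procedural part repeats the split: "collected by sites if not participating in STS or for patients randomized to PCI group".

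Two items under that heading bear on the primary endpoint.

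- **Laboratory Assessment**, marked as partially extracted: "Data regarding the following laboratory values after the index coronary revascularization will be extracted from the clinical registry databases". The list that follows names CK-MB and/or troponin, without draw times and without ECG findings.
- **Hospitalization & MACCE Events**: "Information regarding MACCE events that occur during study-procedure related hospitalizations will also be extracted from the STS registry when possible".

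Other provisions apply to both arms.

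- Treatment Interventions requires biomarkers and an ECG before each procedure. Afterwards it requires a repeat ECG and at least two biomarker draws within 24 hours. The stated purpose is "To minimize ascertainment bias in the identification of peri-procedural MI".
- "Data regarding the index PCI procedure(s) will be provided by the site coordinators", including intra- and post-procedural events, with no restriction by arm.
- "Limited source documentation pertaining to the MACCE event will be collected and uploaded into the EDC".
- A site follow-up takes place 30 (± 7) days after each procedure, with one allowance for early staging.
- An independent Clinical Events Committee (CEC) adjudicates all MACCE.

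**The concern.** The trial is open-label, and peri-procedural MI is a component of the primary endpoint. Its definition needs a pre-procedure value, the peak within 48 hours and, at the lower thresholds, new Q-waves or new LBBB. Many such events could be laboratory findings with no clinical alarm, so whether they count depends on whether the values are recorded and looked at.

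If one arm's values come through a surgical registry, with extraction described as partial and as happening when possible, and the other arm's come through direct site collection, the probability that an event enters adjudication may differ by arm. The plan does not say how the 12-hour and 24-hour values are captured when the registry is the source, what happens when extraction is not possible, or how registry output is reconciled with site records. An in-hospital event missed this way is hard to recover once the trial is over.

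**Working it through.** **Who is affected.** No figure in the plan can be reproduced here, so the first step is to set the provisions side by side.

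| Patient | First-line source of in-hospital MACCE and post-procedure biomarkers |
|---|---|
| HCR, STS site | STS registry (partially, when possible) |
| PCI, STS site | Site collection |
| HCR, non-STS site | Site collection |
| PCI, non-STS site | Site collection |

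Only the first row differs. The Table of Changes notes that most but not all sites will use STS, so that row is not a small one. Within it, the PCI stage of HCR is reported by site coordinators, so the gap is widest for the surgical stage. The schedule's footnote ends STS data at 30 days. Later follow-up to 60 months uses the same telephone method in both arms.

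**What the shared steps recover.** Source-document upload concerns a MACCE already identified, and CEC review works from those documents. The 30-day visit may be omitted after the first procedure, without a violation, if staging occurs before 45 days. The allowance is not limited to one arm, but the plan describes HCR as staged by design and PCI as staged or not. The first visit after the initial procedure could then fall up to 44 + 37 = 81 days later.

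**Illustration of size.** The documents give no capture rate. Inputs from the plan: PCI 5-year MACCE rate 25%; 20% relative reduction, hence 20% in HCR; two-sided α = 0.05; 2354 patients allocated 1:1, hence 1177 per arm. Assumptions: a = 2, 4 or 6 percentage points of MACCE are peri-procedural, and a fraction m = 0.1, 0.2 or 0.3 of these is missed in one arm only.

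*No true difference, misses in HCR only.* The loss is L = a·m/100, and

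SE = √[0.25·0.75/1177 + (0.25 − L)(0.75 + L)/1177].

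The chance of a significant result favouring HCR is P(Z > 1.96 − L/SE). For a = 4, m = 0.2: L = 0.008, SE = 0.01775, L/SE = 0.451, and P(Z > 1.509) = 6.6%. The full grid, against a nominal 2.5%:

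| a (points) | m = 0.1 | m = 0.2 | m = 0.3 |
|---|---|---|---|
| 2 | 3.2% | 4.1% | 5.2% |
| 4 | 4.1% | 6.6% | 10.0% |
| 6 | 5.2% | 10.0% | 17.4% |

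*True 25% vs 20%, a loss of 1 point.* If missed in HCR, the relative risk moves from 0.80 to 0.19/0.25 = 0.76. If missed in PCI, it moves to 0.20/0.24 = 0.83. In the second case, power = Φ[(d − 1.96·SE₀)/SE₁], where SE₀ is the pooled and SE₁ the unpooled standard error of the difference. With d = 0.04, SE₀ = √(2·0.22·0.78/1177) = 0.01708 and SE₁ = √[(0.24·0.76 + 0.20·0.80)/1177] = 0.01706, power is 65%. The same formula without any loss gives 83%. That is a simple comparison of proportions without crossover or loss to follow-up, so it differs from the plan's 80%.

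**The case against.** The case against is substantial.

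- **Scope.** A reader might infer that the primary endpoint as a whole is ascertained differently by arm. The documents do not support that. The difference is confined to index and staged hospitalizations of HCR patients at STS sites. Endpoint definitions, long-term follow-up and adjudication are common to both arms.
- **Contradiction.** A reader might also infer that the plan contradicts its own rule on ascertainment bias. It does not: that rule standardizes testing, and testing is the same in both arms. The unequal data route undercuts the purpose of the rule without breaching it.
- **Direction.** It is tempting to assume that registry capture is the poorer one and that the bias favours HCR. Nothing in the documents shows this. Study Design describes the registry content as clinical data that sites themselves collect for STS.
- **Other routes.** The registry is not presented as the sole source. The schedule legend allows STS data or the site coordinator, and the surgical investigator supplies additional procedure data. Central monitoring focuses on endpoints, completeness and outliers, using uploaded source documents or remote record access. It is not limited to flagged events. The Manual of Procedures, which is not part of these documents, may say more.

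All four points stand as limits on the claim. They do not remove it: no provision states that the timed biomarker values and ECG findings of HCR patients at STS sites are captured as they are for PCI patients, or that the two sources are reconciled before adjudication.

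**Conclusion.** The point holds as a risk of differential detection of in-hospital events at STS sites. It does not establish a bias. The route by which in-hospital MACCE and post-procedure biomarkers first enter the trial depends on assigned arm, and the common safeguards recover some, but not assuredly all, of what that route might miss.

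The false-positive range of about 3-17% rests entirely on the assumed 2-6 peri-procedural points and 10-30% missed, and the low end belongs to it as much as the high end. It is an upper range for three reasons. It applies the miss to every HCR patient, including those at non-STS sites. It treats deaths and strokes as being as easy to miss as enzyme rises. It also subtracts every missed event, although some of these patients would have a later MACCE that counts. Misses in the PCI arm would cost power instead. The case for acting does not depend on the sign: an arm-dependent source for a primary-endpoint component is avoidable at little cost.

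**What to change.** For every index and staged hospitalization, in both arms and at all sites, require the same site-completed trial form. It should cover in-hospital MACCE, the protocol-mandated biomarker values with draw times, and the ECG findings. Keep STS extraction for baseline and surgical descriptors, and use registry-reported events as a cross-check that can only add events for adjudication. State this in Data Collection and in the Manual of Procedures.

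The cost is a change of wording and a few extra fields for HCR patients at STS sites, so a small part of the registry's data-entry saving is lost. Sites must already collect these data for PCI patients and at non-STS sites, although the documents do not show the form itself.
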